Appendix 1: Schedule of Activities

- d [REDACTED]
- e [REDACTED]
- f Vital signs include respiratory rate, pulse rate, systolic and diastolic blood pressure, and temperature. Vital signs should be recorded as described in Section 4.5.5.
- g Complete and limited physical examinations are defined in Section 4.5.4.
- h ECOG Performance Status, a limited physical examination, and specified local laboratory assessments may be obtained ≤ 96 hours before Day 1 of each cycle. Specified assessments performed ≤ 96 hours before Cycle 1, Day 1 for screening are not required to be repeated on Cycle 1, Day 1.
- i ECG recordings will be obtained during screening and as clinically indicated at other timepoints. ECGs for each patient should be obtained from the same machine wherever possible. Lead placement should be as consistent as possible. Patients should be resting in a supine position for at least 10 minutes prior to ECG recording.
- j Hematology includes WBC count, RBC count, hemoglobin, hematocrit, platelet count, and differential count (neutrophils, eosinophils, basophils, monocytes, lymphocytes).
- k Chemistry panel (serum or plasma) includes bicarbonate or total carbon dioxide (if considered SOC for the region), sodium, potassium, chloride, glucose, BUN or urea, creatinine, total protein, albumin, phosphate, calcium, total bilirubin, ALP, ALT, AST, and LDH.
- l All women of childbearing potential will have a serum pregnancy test at screening, within 14 days prior to Cycle1, Day1. Urine pregnancy tests must be performed on Day 1 of every cycle and at end of treatment visit. If a urine pregnancy test is positive, it must be confirmed by a serum pregnancy test.
- m TSH, free T3 (or total T3 for sites where free T3 is not performed), and free T4 will be collected at screening, on Day 1 of Cycle 1, and every fourth cycle thereafter (i.e., Cycles 5, 9, 13, etc.). [REDACTED]
- n A [REDACTED]

Appendix 1: Schedule of Activities

- o [REDACTED]
- p Includes pH, specific gravity, glucose, protein, ketones, and blood; dipstick permitted.
- q Concomitant medications include prescription drugs, over-the-counter drugs, vaccines, herbal or homeopathic remedies, nutritional supplements. Any medications the patient has used within 7 days prior to initiation of study treatment should be documented. At subsequent visits, changes to current medications or medication used since the last document will be recorded.
- r Tumor assessments performed as SOC prior to obtaining informed consent may be used rather than repeating tests provided the scans are of diagnostic quality and are performed within 28 days of randomization. All known sites of disease, including measurable and/or non-measurable disease, must be documented at screening and re-assessed at each subsequent tumor evaluation. The same radiographic modality (e.g., computed tomography [CT] scan with contrast) and procedures (e.g., the same contrast protocol for CT scans) used at screening must be used for all subsequent tumor assessments. Screening assessments and subsequent tumor assessments must include CT scans (with oral or IV contrast) of the chest and abdomen and CT scans (with oral or IV contrast) or magnetic resonance imaging (MRI) (with contrast) of the head and neck (base of skull to clavicle). A CT scan with contrast of the pelvis should be performed as clinically indicated, or as per local SOC, at screening, and subsequent response evaluations. If a CT scan with contrast is contraindicated (e.g., in patients with impaired renal clearance), a non-contrast CT scan of the chest may be performed, and MRI scans with contrast of the head and neck, abdomen, and pelvis (as applicable) must be performed. Further investigations, such as bone scans should also be performed, if clinically indicated, at baseline and at subsequent response evaluations. A CT scan with contrast or MRI scan with contrast (if CT with contrast is contraindicated) of the brain should be done as clinically indicated to evaluate CNS metastasis at screening and at subsequent response evaluations. If a CT scan with contrast is performed and the presence of brain metastases is considered equivocal, an MRI scan of the head is required to confirm or refute the diagnosis of CNS metastases at baseline. Patients with active or untreated CNS metastases are not eligible for the study (see Section 4.1.2). Patients with a history of irradiated brain metastasis at screening are not required to undergo head scans at subsequent response evaluations unless clinically indicated. If a CT scan for tumor assessment is performed in a positron emission tomography/CT scanner, the CT acquisition must be consistent with the standards for a full-contrast diagnostic CT scan.

Appendix 1: Schedule of Activities

- ^s Patients will undergo tumor assessments at baseline, every 6 weeks (± 7 days) for the first 30 weeks following Day 1 of Cycle 1, and every 9 weeks (± 7 days) after completion of the Week 30 tumor assessment. Tumor assessments will continue per schedule, regardless of treatment delays, until radiographic disease progression per RECIST v1.1 or loss of clinical benefit for patients who continue study treatment after radiographic disease progression per RECIST v1.1, withdrawal of consent, death, or study termination by the Sponsor, whichever occurs first. At the investigator's discretion, scans must also be performed at any time if progressive disease or loss of clinical benefit is suspected. Patients who discontinue study treatment (for any reason, including, but not limited to, clinical decline or toxicity) in the absence of radiographic disease progression per RECIST v1.1 will continue to undergo tumor response assessments until radiographic disease progression per RECIST v1.1, withdrawal of consent, death, or study termination by the Sponsor, whichever occurs first. In the absence of radiographic disease progression per RECIST v1.1, tumor assessments should continue regardless of whether a patient starts a new anti-cancer therapy.
- ^t After informed consent has been obtained but prior to initiation of study treatment, only serious adverse events caused by a protocol-mandated intervention should be reported. After initiation of study treatment, all adverse events will be reported until [REDACTED] days after the final dose of study treatment [REDACTED] and serious adverse events will continue to be reported until [REDACTED] days after the final dose of study treatment [REDACTED]. In addition, adverse events of special interest will continue to be reported until [REDACTED] days after the final dose of study treatment, [REDACTED]. After this period, all deaths, regardless of cause, should be reported. In addition, the Sponsor should be notified if the investigator becomes aware of any serious adverse event that is believed to be related to prior exposure to study treatment (see Section 5.6).
- ^u Specified screening laboratory test results must be obtained within 14 days prior to randomization.
- ^v PRO assessments: Patient-Reported Outcomes Measurement Information System® [PROMIS®] Item Bank v2.0–Physical Functioning–Short Form 10b, [REDACTED] Patient Global Impression of Severity, Patient Global Impression of Change and its Importance, Most Important Symptoms, and Patient-Reported Outcomes Common Terminology Criteria for Adverse Events will be completed before the patient receives any information on disease status and prior to the performance of non-PRO assessments and the administration of study treatment. Study personnel should review all questionnaires for completeness before the patient leaves the investigational site. See Appendix 2 for schedule of PRO assessments.
- ^x Patients should receive their first dose of study drug the day of randomization, if possible. [REDACTED]. Atezolizumab will be administered prior to tiragolumab/placebo. Patients will receive atezolizumab by continuous IV infusion every 21 days on Day 1 of each 21-day cycle as indicated. For atezolizumab, the initial dose will be delivered over 60 (± 15) minutes. If the first infusion is well tolerated, all subsequent infusions may be delivered over 30 (± 10) minutes. Following atezolizumab, patients will receive tiragolumab or placebo by continuous IV infusion every 21 days on Day 1 of

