4.3.2.1 Atezolizumab

All patients will receive 1200 mg atezolizumab administered by IV infusion on Day 1 of each 21-day cycle (see Section 3.1). The atezolizumab dose is fixed and is not dependent on body weight.

Atezolizumab infusions will be administered per the instructions outlined Table 1.

No dose modification for atezolizumab is allowed. Guidelines for treatment interruption or discontinuation are provided in Section 4.6.1, Section 5.1.4, and Appendix 16.

For further details on dose preparation, storage, and administration instructions for atezolizumab, refer to the pharmacy manual and/or the Atezolizumab Investigator's Brochure.

Table 1 Administration of First and Subsequent Atezolizumab Infusions

	Day 1, Cycle 1 Infusion	Day 1 Infusion of Subsequent Cycles
Atezolizumab infusion	
• No premedication is permitted prior to the atezolizumab infusion.• Vital signs (pulse rate, respiratory rate, blood pressure, and temperature) should be recorded within 60 minutes prior to the infusion.• Atezolizumab should be infused over 60 (\pm 15) minutes.• If clinically indicated, vital signs should be recorded every 15 (\pm 5) minutes during the infusion.	
• If the patient experienced an IRR with any previous infusion of atezolizumab, premedication with an antihistamine and/or antipyretic medications may be administered for subsequent doses at the discretion of the investigator.• Vital signs should be recorded within 60 minutes prior to the infusion.• Atezolizumab should be infused over 30 (\pm 10) minutes if the previous infusion was tolerated without an IRR or 60 (\pm 15) minutes if the patient experienced an IRR with the previous infusion.• If the patient experienced an IRR with the previous infusion, or if clinically indicated, vital signs should be recorded during the infusion.

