Observation period after atezolizumab infusion	
• After the infusion of atezolizumab, the patient begins a 60-minute observation period.• Vital signs should be recorded at 30 (\pm 10) minutes after the infusion of atezolizumab.• Patients will be informed about the possibility of delayed post-infusion symptoms and instructed to contact their study physician if they develop such symptoms.	
• If the patient tolerated the previous atezolizumab infusion well without infusion-associated adverse events, the observation period after the next and following infusions may be reduced to 30 minutes.• If the patient experienced infusion-associated adverse events in the previous infusion, the observation period should be 60 minutes.• If clinically indicated, vital signs should be recorded at 30 (\pm 10) minutes after the infusion of atezolizumab.

IRR = infusion-related reaction.

Guidelines for medical management of IRRs are provided in the Appendix 16.

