4.3.2.2 Tiragolumab/Placebo

Following the administration of atezolizumab and an observation period (see [Table 1](#)), patients will receive 600 mg tiragolumab/placebo administered by IV infusion on Day 1 of each 21-day cycle (see Section [3.1](#)). The tiragolumab/placebo dose is fixed and is not dependent on body weight.

Tiragolumab/placebo infusions will be administered per the instructions outlined in [Table 2](#).

No dose modification for tiragolumab/placebo is allowed. Guidelines for treatment interruption or discontinuation are provided in Section [4.6.1](#), Section [5.1.4](#), and [Appendix 16](#).

For further details on dose preparation, storage, and administration instructions for tiragolumab/placebo, refer to the pharmacy manual and/or the Tiragolumab Investigator's Brochure.

Table 2 Administration of First and Subsequent Infusions of Tiragolumab/Placebo

	Day 1, Cycle 1 Infusion	Day 1 Infusion of Subsequent Cycles
Infusion of tiragolumab/ placebo	
 No premedication is permitted prior to the tiragolumab/ placebo infusion. Vital signs (pulse rate, respiratory rate, blood pressure, and temperature) should be recorded within [REDACTED] minutes prior to the infusion. Tiragolumab/placebo should be infused over [REDACTED] minutes. Vital signs should be recorded every [REDACTED] minutes during the infusion. 	
 If the patient experienced an IRR during any previous infusion of tiragolumab/placebo, [REDACTED] may be administered for subsequent doses, at the discretion of the investigator. Vital signs should be recorded within [REDACTED] minutes prior to the tiragolumab/placebo infusion. Tiragolumab/placebo should be infused over [REDACTED] minutes if the previous infusion was tolerated without an infusion-related reaction, or [REDACTED] minutes if the patient experienced an infusion-related reaction with the previous infusion. Vital signs should be recorded during the infusion if clinically indicated.

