Observation period after infusion of tiragolumab/ placebo	
 After the infusion of tiragolumab/placebo, the patient begins a [REDACTED] minute observation period. Vital signs should be recorded at [REDACTED] minutes after the infusion of tiragolumab. Patients will be informed about the possibility of delayed post-infusion symptoms and will be instructed to contact their study physician if they develop such symptoms. 	
 If the patient tolerated the previous infusion of tiragolumab/placebo well without infusion-associated adverse events, the observation period may be reduced to [REDACTED] minutes. If the patient experienced an infusion-associated adverse event in the previous infusion, the observation period should be [REDACTED] minutes. If clinically indicated, vital signs should be recorded at [REDACTED] minutes after the infusion of tiragolumab/placebo. Patients will be informed about the possibility of delayed post-infusion symptoms and will be instructed to contact their study physician if they develop such symptoms.

IRR = infusion-related reaction.

Guidelines for medical management of IRRs are provided in [Appendix 16](#).

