5.1.2.1 Infusion-Related Reactions

Because tiragolumab is a therapeutic MAb and targets tumor-infiltrating ICs, IRRs associated with hypersensitivity reactions and/or target-mediated cytokine release may occur. Clinical signs and symptoms of such reactions may include rigors, chills, wheezing, pruritus, flushing, rash, hypotension, hypoxemia, and fever.

IRRs have been reported in patients treated with tiragolumab with or without atezolizumab. The majority of events were mild to moderate and manageable.

To minimize the risk and sequelae of IRRs, the initial dose of tiragolumab/placebo will be administered over [REDACTED] minutes followed by a [REDACTED] minute observation period, and subsequent infusions as well as observation times may be shortened only if the preceding infusion was well tolerated. All infusions will be administered in an appropriate medical setting.

Refer to Sections [4.3.2.1](#) and [4.3.2.2](#) for detailed guidance on administration of atezolizumab and tiragolumab/placebo in this study. Refer to [Appendix 15](#) for guidance on anaphylaxis precautions, and see [Appendix 16](#) for guidance on management of IRRs and risks associated with tiragolumab.

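### Appendix 1 footnote x lets all later infusions be shortened if the first was tolerated, while Tables 1 and 2 and Section 5.1.2.1 look to the infusion just before

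*Combined protocol and SAP*

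**What the plan says.** Infusion duration is addressed in three places.

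- **Appendix 1, footnote x.** After a first atezolizumab infusion over 60 (± 15) minutes: "If the first infusion is well tolerated, all subsequent infusions may be delivered over" 30 (± 10) minutes. The same sentence follows for tiragolumab/placebo, with the minutes redacted. The visible text makes no exception for a reaction at a later cycle.
- **Section 4.3.2, Tables 1 and 2.** For cycles after the first, Table 1 gives atezolizumab over 30 (± 10) minutes when the previous infusion caused no IRR, and over 60 (± 15) "minutes if the patient experienced an IRR with the previous infusion". Table 2 has the same structure for tiragolumab/placebo: a redacted time after a tolerated infusion, and another redacted time, in "minutes if the patient experienced an infusion-related reaction with the previous infusion". The observation periods look back in the same way. Table 1 says "If the patient experienced infusion-associated adverse events in the previous infusion, the observation period should be 60 minutes", and Table 2 says "If the patient experienced an infusion-associated adverse event in the previous infusion, the observation period should be" a redacted number of minutes.
- **Section 5.1.2.1.** For tiragolumab/placebo, "subsequent infusions as well as observation times may be shortened only if the preceding infusion was well tolerated".

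**The concern.** Footnote x sets one condition, met or failed at Cycle 1, and lets it govern every later cycle. The tables reset the condition at each cycle. The two agree on the trigger only at Cycle 2, where the first infusion is also the previous one.

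The unsafe direction is a patient who tolerates Cycle 1 and reacts later. Read alone, footnote x allows the faster infusion straight after that reaction. Table 1 does not allow this for atezolizumab, and Section 5.1.2.1 does not allow it for tiragolumab/placebo.

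Appendix 1 is a working document for sites: Section 4.5 sends them there for the activities to be performed. Several other footnotes point to the section that governs them (f to Section 4.5.5, g to Section 4.5.4, v to Appendix 2). The visible text of footnote x gives infusion times itself and has no pointer to Table 1 or Table 2. The stake is patient safety at the infusion visit, not inference.

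**Working it through.** The plan has no figure to reproduce here. The check is a side-by-side reading, followed by simple arithmetic for atezolizumab.

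**Inputs.** Dose 1200 mg, fixed (Section 4.3.2.1). Short infusion 30 (± 10) minutes and long infusion 60 (± 15) minutes (Table 1; footnote x gives the same two times).

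**Worked cases, atezolizumab at Cycle 3**

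| Cycle 1 | Cycle 2 | Footnote x | Table 1 |
|---|---|---|---|
| tolerated | tolerated | 30 (± 10) permitted | 30 (± 10) |
| tolerated | IRR | 30 (± 10) permitted | 60 (± 15) |
| IRR | tolerated | condition for shortening not met | 30 (± 10) |

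The second row is the unsafe conflict. The third row is a conflict in the other direction, with footnote x the stricter text.

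**Size of the conflict in the second row**

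- Windows: 30 ± 10 gives 20 to 40 minutes; 60 ± 15 gives 45 to 75 minutes. They do not overlap.
- Nominal rates: 1200/30 = 40 mg/min against 1200/60 = 20 mg/min, a ratio of 2.0.
- Rates across the windows: 1200/20 = 60.0 down to 1200/40 = 30.0 mg/min for the short infusion; 1200/45 = 26.7 down to 1200/75 = 16.0 mg/min for the long one.
- Difference in duration: smallest 45 − 40 = 5 minutes, largest 75 − 20 = 55 minutes.
- Rate ratio: smallest 45/40 = 1.125, largest 75/20 = 3.75.

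**Tiragolumab/placebo.** All durations are redacted, so no difference can be computed. The triggers are visible and conflict in the same way: first infusion in footnote x, previous infusion in Table 2, preceding infusion in Section 5.1.2.1.

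**How many patients.** The documents do not give this. Section 1.6.2.2 reports IRRs in 28.4% and 10.3% of patients in the two arms of the Phase II NSCLC study. If those rates carried over to 80 and 40 patients (2:1 of 120), the expected number with an IRR would be 0.284 × 80 + 0.103 × 40 = 22.7 + 4.1 = 26.8, about 27. How many of them would first react after Cycle 1 is unknown and could be anything from 0 to 27.

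**The case against.** The strongest reply is that the dosing sections already govern. Section 4.3.2.1 states "Atezolizumab infusions will be administered per the instructions outlined Table 1", Section 4.3.2.2 states "Tiragolumab/placebo infusions will be administered per the instructions outlined in" Table 2, and Section 5.1.2.1 refers readers to both sections for administration detail. Footnote x is a permissive summary, so a site following the tables breaches nothing in it. This stands and limits the harm. It does not remove the conflict, because what footnote x permits is exactly what the other texts exclude.

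The trigger is also narrow. It needs a tolerated Cycle 1, a later IRR, re-treatment, and a site relying on the footnote instead of the table. Other safeguards remain in place: a monitored setting, toxicity assessment before each dose, optional premedication after an earlier IRR, vital signs during the atezolizumab infusion after a previous IRR, and the longer observation period after atezolizumab. Footnote x does not alter any of these, and it says nothing about observation, so the observation rules show the tables' logic but are not themselves contradicted. All of this supports a low rating.

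Finally, some relevant text cannot be seen. The pharmacy manual is not among the documents, Appendix 16 Table 7 on IRR management is redacted, and footnote x has a redacted portion before its infusion text. Any of these might add instructions, and no claim is made about their content. The visible introduction to Table 7 concerns IRRs during Cycle 1, whereas this conflict arises from one at Cycle 2 or later.

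**Conclusion.** The inconsistency is real on the current text, and neither redaction nor the amendment summary explains it. For atezolizumab after a later-cycle IRR, footnote x permits an infusion at nominally twice the rate that Table 1 calls for, in a time window that does not overlap Table 1's. For tiragolumab/placebo the conflict of triggers is certain, but its size cannot be stated.

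This is a minor safety-instruction error that should be corrected. The conclusion assumes that Tables 1 and 2 are the intended rule, as the dosing sections indicate, and that nothing in the unseen text overrides footnote x. The practical effect is probably small. No endpoint, sample size or planned analysis is affected.

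**What to change.** In Appendix 1 footnote x, replace the atezolizumab sentence with wording to this effect: *each later infusion should run over 30 (± 10) minutes if the one before it was tolerated without an IRR, and over 60 (± 15) minutes if the one before it caused an IRR (see Table 1).* Replace the tiragolumab/placebo sentence in the same form, using the two Table 2 durations and citing Table 2. Deleting both sentences and leaving only a reference to Tables 1 and 2 would also resolve the conflict, and would avoid keeping the rule in two places.

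The cost is two footnote sentences at the next amendment. Any site now following footnote x would spend nominally 60 − 30 = 30 more minutes on the atezolizumab infusion after a reaction. No procedure, data item or analysis changes.

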Appendix 1: Schedule of Activities

each 21-day cycle as indicated. For tiragolumab or placebo, the initial dose will be delivered over [REDACTED] minutes. If the first infusion is well tolerated, all subsequent infusions may be delivered over [REDACTED] minutes.

- ^y Only collected on Day 1 of Cycle 1 prior to the first dose of study treatment.
- ^z Not applicable for a site that has not been granted approval for RBR sampling. Performed only for patients at participating sites who have provided written informed consent to participate.
- ^{aa} Patients will undergo tumor biopsy sample collection, if deemed clinically feasible by the investigator, at the time of first evidence of radiographic disease progression per RECIST v1.1. Biopsies should be performed within 40 days after progression or prior to the next anti-cancer therapy, whichever is sooner. See Section 4.5.7 for tissue sample requirements.
- ^{bb} After treatment discontinuation, information on survival follow-up and new anti-cancer therapy (including targeted therapy and immunotherapy) will be collected via telephone calls, patient medical records, and/or clinic visits approximately every 3 months until death, unless the patient withdraws consent or the Sponsor terminates the study. If a patient requests to be withdrawn from survival follow-up, this request must be documented in the source documents and signed by the investigator. If the patient withdraws from the study (i.e., survival follow-up), the study staff may use a public information source (e.g., county records) to obtain information about survival status.

[figure not shown]
